6.3.1.7 Adverse events of special interest

Adverse events of special interest will be separately analysed and closely monitored throughout the course of the study for safety reasons.

Adverse events of special interests are defined as myocardial infarction, haemorrhage, hypotension, haemoptysis, syncope and stroke.

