9.1.1. Incidence of Treatment Emergent Adverse Events

A treatment-emergent adverse event (TEAE) is defined as any event not present before exposure to study drug or any event already present that worsens in either intensity or frequency after exposure to study drug. If start date of an AE is missing after imputation, the corresponding AE will be included as TEAE if end date of AE is after the first dose of study drug or the end date is also missing. Imputation for partial AE start dates and end dates can be found in Appendix 13.4.

The number and percentage of patients with at least one TEAE will be summarised by MedDRA system organ class (SOC) and preferred term (PT). At each level of SOC or PT, a patient will be counted only once if the patient reported multiple events.

The above analysis will also be conducted for TEAEs occurred from V0 to V3 and by subgroups as defined in section 4.4.

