9.1.7. TEAEs of Special Interest

The following TEAEs of special interest will be defined and included in summary tables by treatment group:

MedDRA coding

- “Myocardial infarction” and “Acute myocardial infarction” as preferred term;
- “Haemorrhage” will be assessed by using the standardised MedDRA query (SMQ);
- “Hypotension”, “haemoptysis”, “syncope” will be assessed as preferred term;
- “Stroke” will be assessed by using the preferred terms “haemorrhagic stroke”, “ischaemic stroke” and “embolic stroke”.

The TEAEs of special interest will be summarized by group: Myocardial infarction, Haemorrhage, Hypotension, Haemoptysis, Syncope, Stroke and also by study period V0 to V2, V0 to V4, medication of interest subgroup as defined in Section 4.4. The number of patients along with number of events in each level of summary will be provided.

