13.3. Surgery-related complications

Surgery-related complications are defined as the following:

- Bleeding and/or blood loss >1 L in 12 hours
- Airway bleed with need for extracorporeal membrane oxygenation
- Any use of extracorporeal membrane oxygenation for respiratory or haemodynamic support, specified as veno-venous or veno-arterial
- Prolonged ventilation >96 hours
- Need for tracheostomy
- Need for drainage of pericardial effusion
- Neurological complications, ie, stroke, cerebral, subdural bleeding
- Reintubation or noninvasive ventilation for reperfusion response
- Haemoptysis requiring any intervention
- Renal failure requiring dialysis
- Wound infections
- Pneumonia
- Prolonged need for inotropic support (≥ 5 days)

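### SAP 9.1.7 counts stroke only under three subtype terms, so a stroke with no recorded subtype drops out of the special-interest stroke summary that the protocol requires

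*SAP*

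**What the plan says.** Protocol 6.3.1.7 lists six categories: "Adverse events of special interests are defined as myocardial infarction, haemorrhage, hypotension, haemoptysis, syncope and stroke". It also sets what is to be done with them: "Adverse events of special interest will be separately analysed and closely monitored throughout the course of the study for safety reasons". Stroke appears there without qualification.

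SAP 9.1.7 turns each category into a coding rule:

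- Stroke: "Stroke” will be assessed by using the preferred terms “haemorrhagic stroke”, “ischaemic stroke” and “embolic stroke".
- Myocardial infarction: "Myocardial infarction” and “Acute myocardial infarction” as preferred term".
- Haemorrhage: "Haemorrhage” will be assessed by using the standardised MedDRA query (SMQ").
- Hypotension, haemoptysis and syncope: the preferred term of the same name.

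The section then fixes the reporting groups: "The TEAEs of special interest will be summarized by group: Myocardial infarction, Haemorrhage, Hypotension, Haemoptysis, Syncope, Stroke". These are also to be split by study period (V0 to V2 and V0 to V4) and by the concomitant-medication subgroups of SAP 4.4. SAP 9.1 adds an overall count of patients with any treatment-emergent event of special interest.

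**The concern.** The SAP definition of stroke is narrower than the protocol's. It is a closed list of subtypes with no general stroke term, no standardised query and no rule for a stroke whose type is not recorded. Followed as written, it leaves out events that the protocol says belong in the separate analysis.

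What is at stake is the Stroke line of the special-interest tables, its splits, and the overall special-interest count. Stroke is a relevant harm here: patients must be anticoagulated (Protocol 5.8), and circulatory arrest time is recorded as part of the operation (Protocol 6.2.7). Amendment 2 added the special-interest list expressly to strengthen safety monitoring.

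**Working it through.** The point rests on comparing texts. No sample size, power or alpha figure is involved, so the plan has no figure to reproduce.

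**1. Definition against coding rule.**

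| Category | Protocol 6.3.1.7 | SAP 9.1.7 | General term covered? |
|---|---|---|---|
| Myocardial infarction | unqualified | general term plus acute form | yes |
| Haemorrhage | unqualified | standardised query | broad search |
| Hypotension | unqualified | same-named term | yes |
| Haemoptysis | unqualified | same-named term | yes |
| Syncope | unqualified | same-named term | yes |
| Stroke | unqualified | haemorrhagic, ischaemic, embolic | no |

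Stroke is the only category built from subtypes with the general term left out. The conclusion does not depend on which MedDRA term an untyped stroke would receive, because an event with no recorded subtype fits none of the three listed terms on their wording.

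**2. Is the narrowing declared?** SAP Section 11 lists changes from the protocol. It covers analysis sets, a laboratory summary, the composite endpoint period, a therapy endpoint and the visit for specimen evaluation. It does not mention stroke.

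**3. Could an untyped stroke occur?** The adverse event items in Protocol 6.3.1.3 include an event term but no stroke subtype. The documents also use the unqualified word elsewhere, in SAP 13.3: "Neurological complications, ie, stroke, cerebral, subdural bleeding". That list belongs to a separate surgical endpoint and does not show how adverse events will be coded. It shows only that the plan treats stroke without a type as recordable.

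**4. Where would such an event go?** It is missing from the Stroke group, from that group's period and medication splits, and from the overall count in SAP 9.1 unless the patient has another listed event. The haemorrhage query might catch a bleeding event, but under Haemorrhage, and its contents are not in the documents.

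The event remains in the general table of SAP 9.1.1: "The number and percentage of patients with at least one TEAE will be summarised by MedDRA system organ class (SOC) and preferred term (PT"). It also remains in the relatedness and severity tables, the serious-event tables if serious (SAP 9.1.4), the listings (SAP 9.1) and, if perioperative, the complications table (SAP 8.2.3.2).

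**5. Illustration under assumed rates.** Let p be the risk of stroke per patient and f the share of strokes with no recorded subtype. Neither is in the documents. With N = 88 planned patients (SAP 4.1):

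- Expected strokes = N × p.
- Expected strokes missed = N × p × f.
- Probability that at least one is missed = 1 − (1 − p × f)^N.

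| p | f | Expected strokes | Expected missed | P(at least one missed) |
|---|---|---|---|---|
| 1% | 10% | 0.88 | 0.09 | 8% |
| 3% | 30% | 2.64 | 0.79 | 55% |
| 5% | 50% | 4.40 | 2.20 | 89% |

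For the effect of one omission, assume 3 strokes among the 44 patients planned per arm (88 / 2), one of them untyped. The Stroke line would show 2/44 = 4.5% instead of 3/44 = 6.8%. The actual denominator is the safety set, meaning patients who took study drug, so it may differ from 44.

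**The case against.** The strongest reply is that little is lost. An untyped stroke still appears by treatment group in several tables. A perioperative one is captured without any subtype among the surgical complications, and SAP 8.2.3.2 compares those between arms with a Fisher exact test, whereas SAP 9.1.7 asks only for counts. An unblinded safety board reviews safety data during the trial. All analyses are exploratory (Protocol Section 7), and no test or decision rule uses the special-interest stroke count. How often a stroke would go untyped cannot be known from the documents.

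Most of this stands, and it limits the point. A reader might infer that strokes disappear from the safety evaluation, or that these tables are the main check for harm. The documents support neither: the events remain visible elsewhere, and nothing ranks the special-interest tables above the rest.

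The reply does not remove the gap, because the protocol asks for stroke to be analysed separately and none of the other outputs does that. Preferred-term tables show terms one by one. The complications table covers only surgery-related events, groups stroke with intracranial bleeding, and would not show a stroke before surgery on study drug.

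A reader might also extend the criticism to hypotension, since the titration rule in Protocol 5.2 mentions dizziness and presyncope, or to syncope. The documents do not support this. For both, the SAP term matches the protocol's word. Protocol 5.2 uses those symptoms together with a systolic pressure below 95 mmHg to choose a dosing step, not to define hypotension as an adverse event. Protocol 1.4 reports dizziness and hypotension as separate events (16.4% and 11.9% in the riociguat 2.0 mg group of Study 14308).

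**Conclusion.** The concern holds for stroke alone. SAP 9.1.7 contains a stated rule that misses events the protocol includes, and the SAP does not declare the narrowing. The consequence is confined to the Stroke group, its period and subgroup splits, and possibly the overall special-interest count.

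Its size is unknown. The assumed ranges give a chance of missing at least one stroke anywhere from 8% to 89%, which shows that the documents cannot settle it. The reason to act is that, if the number of strokes is small as those ranges assume, a single omission could change a descriptive comparison between arms. The finding assumes only that some stroke may be reported without a subtype.

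**What to change.** Before database lock and unblinding, amend SAP 9.1.7 in one of two ways:

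- define stroke by a named standardised MedDRA query, as is already done for haemorrhage, after confirming that it covers strokes of unspecified type; or
- fix a list of preferred terms at blinded review that keeps the three subtypes and adds a general, unspecified-type stroke term.

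Record the chosen definition in the SAP. If the three-term list is kept on purpose, state and justify the departure from Protocol 6.3.1.7 in SAP Section 11. No change is needed to the hypotension or syncope rules on this account.

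The cost is a wording change and, for the second option, one blinded term review. No new data are needed. The downside is that a broader query may bring in a few non-specific events.

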7.8.4 Safety Analyses

Safety analysis except by-visit summarisations will be presented in 2 ways, one based on only the assessments during the double blind treatment phase, and another based on the assessments during the whole study.

Adverse events will be summarised by presenting for both treatment groups the number and percentage of patients having any AE, having an AE in each MedDRA primary system organ class, and having each individual AE (preferred term). Additionally, a summary of AEs by preferred term and severity will be performed using the worst severity grade.

All related AEs, AEs with outcome death, AEs leading to permanent discontinuation of treatment, SAEs, and related SAEs will be summarised by percentages and frequencies and listed including the investigator term, the preferred term, start and end dates of the AE, duration (days), severity, drug relationship, action taken, and outcome.

Treatment-related AEs are those rated by the investigator as “definite,” “probable,” or “possible.” In case the relationship is unknown or missing, the worst case will be assumed and the AE will be considered to be drug related.

For laboratory data, the proportion of patients with clinically significant abnormal values as reported by the investigator will be provided by laboratory parameter, dose cohort, and scheduled visit.

For each laboratory parameter, shift tables of baseline categories based on normal ranges (below, within, above) versus categories at each postbaseline scheduled visit and the worst postbaseline value will be provided.

Summary statistics of values and changes from baseline over time will be computed for all safety laboratory parameters.

For vital sign measurements, supine or seated blood pressure and HR (absolute values and change from baseline) will be summarised by dose cohort and scheduled visit.

For ECGs, the proportion of patients with a clinically significant abnormal ECG result will be provided. A summary of shifts in 12-lead ECG abnormalities from baseline will be provided by scheduled visits.

Abnormal physical examination data will be summarised by treatment group and body system with number and percentage of patients.

Previous and concomitant treatments coded using the WHO Drug Dictionary and medical history coded using MedDRA will be summarised by treatment group number and percentage of patients at different coded terms.

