2.2. Secondary Objectives

The secondary objectives of this study are the following:

- To assess the efficacy of riociguat on other preoperative pulmonary haemodynamic parameters in patients with operable CTEPH
- To assess the efficacy of riociguat on postoperative pulmonary haemodynamic parameters in patients with operable CTEPH
- To assess the effect of riociguat on safety and efficacy aspects during PEA in patients with operable CTEPH
- To assess the safety and tolerability of riociguat in patients with operable CTEPH

[figure not shown]
3. Investigational Plan

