3.1. Overall Study Design and Plan

This is a randomised, double-blind, placebo-controlled, multicentre, multinational, prospective study in patients with operable CTEPH prior to PEA with high preoperative PVR (>800 $\text{dyn}\cdot\text{s}\cdot\text{cm}^{-5}$). Eligible patients will be randomly assigned to riociguat or matching placebo 3 times a day (tid) in a 1:1 ratio. A total of 88 patients are planned to randomly assign at 4 sites in North America and Europe.

A schematic of the study design is presented in Figure 3-1.

Figure 3-1 Study Schematic

Abbreviations: PEA, pulmonary endarterectomy; RHC, right heart catheterisation; V, visit

Patients will undergo a screening period of up to 89 days prior to baseline (Visit 1). Following completion of the pretreatment screening phase, eligible study patients will be randomly assigned into the study.

The study will comprise 3 study periods:

- **Screening Period (Day -89 to Day 1):** The screening period of up to 90 days will be used to assess eligibility of patients and to allow for the washout of prohibited medications. Screening visit (V0) and randomisation visit (V1) can occur on the same day.
- **Treatment Period (Day 1 [Baseline] through Day 90):** Patients will be randomly assigned on Day 1 to receive either riociguat or matching placebo tid in a 1:1 ratio for 3 months. The study drug will be initiated at 1 mg and the dosage can be increased by 0.5 mg at 2-week intervals based on tolerability (systolic blood pressure [SBP]) up to a maximum dose of 2.5 mg tid based on the algorithm mentioned in Section 3.4. The study drug will be initiated no later than 180 days after right heart catheterisation (RHC) (used for screening of patients) and within 90 days of planned RHC before PEA. At Visit 2, RHC will be performed per site procedures no more than 1 week prior to PEA, which will be conducted by the principal surgeon of the site. The study drug will be discontinued once PEA is performed. The last study dose will be given on the morning of PEA surgery. The patient will remain hospitalised per the investigator's discretion.
- **Follow-up Period:** A follow-up visit is planned at 6 months after PEA, at which time RHC will also be performed per study site procedures.

A telephonic call visit is planned during treatment period and at Day 186±10 during follow-up period, where treating physician or designee will call patient to ask questions related to patient's well-being and any adverse events.

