9.1. Adverse Events

An adverse event (AE) is defined as any untoward medical occurrence in a patient enrolled into this study regardless of its causal relationship to study drug. Adverse events will be assessed from the time the patient signs the ICF until exit from the study. In addition to patient observations, AEs identified from any study data (eg, laboratory values, physical examination findings, ECG changes) or identified from review of other documents that are relevant to patient safety will be defined as AEs and recorded appropriately. All AEs reported or observed during the study will be recorded on the AE page in the eCRF. Adverse events will be coded using MedDRA (Version 20.1 or higher).

An overall summary of the number and percentage of patients having any treatment emergent adverse event (TEAE), serious TEAE, treatment-related TEAE, treatment-related serious TEAE, TEAE leading to permanent discontinuation of treatment, TEAE leading to study discontinuation, TEAE with outcome death, and TEAE of special interest will be provided by treatment group. All AEs will be listed including the investigator term, the preferred term, start and end dates of the AE, duration (days), severity, drug relationship, action taken, and outcome for all screened patients.

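### The shorter window for adverse events of special interest ends at Visit 2 rather than at the last dose, and no such table separates the perioperative period from follow-up

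*SAP*

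**What the plan says.** SAP 9.1.7 defines six AESI groups (myocardial infarction, haemorrhage, hypotension, haemoptysis, syncope, stroke) and tabulates them by group and "also by study period V0 to V2, V0 to V4, medication of interest subgroup as defined in Section 4.4". The overall summary in SAP 9.1 adds one AESI count with no split by period: "TEAE with outcome death, and TEAE of special interest will be provided by treatment group".

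The other adverse event sections, SAP 9.1.1 to 9.1.6, use a different restricted period. SAP 9.1.1 reads: "The above analysis will also be conducted for TEAEs occurred from V0 to V3 and by subgroups as defined in section 4.4".

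On timing, SAP 3.1 states that at Visit 2 "RHC will be performed per site procedures no more than 1 week prior to PEA", and that "The last study dose will be given on the morning of PEA surgery".

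Protocol 7.8.4 asks for safety results, apart from by-visit summaries, in two forms: "one based on only the assessments during the double blind treatment phase, and another based on the assessments during the whole study". One of the secondary objectives in SAP 2.2 is "To assess the effect of riociguat on safety and efficacy aspects during PEA in patients with operable CTEPH".

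SAP section 11, which lists departures from the protocol's analyses, mentions none of the safety periods.

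**The concern.** The AESIs are the events singled out for separate analysis and close monitoring (protocol 6.3.1.7), yet their restricted window is the shortest in the safety section. Patients are still taking study drug after the Visit 2 catheterisation and are operated on within hours of a dose. Hypotension, bleeding, haemoptysis, stroke or infarction in those last days, or during the operation, would fall outside the V0 to V2 table. They would appear only in the V0 to V4 table, mixed with about 6 months without drug. A difference between arms close to or during surgery could be diluted there, although safety during PEA is a stated objective.

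**Working it through.** **Inputs**
- Visit 2: Day 90, up to Day 120. Visit 3: Day 96. Visit 4: Day 276 ± 10 (SAP 13.1).
- Catheterisation to PEA: at most 7 days (SAP 3.1).
- Last dose: the day of PEA (SAP 3.1).
- Assumption: V2 in SAP 9.1.7 means the date of the Visit 2 catheterisation. The SAP gives no cut date.

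**1. Check of the calendar.** Nominal interval from Visit 2 to Visit 3: 96 − 90 = 6 days, within the 1-week limit. 276 − 96 = 180 days, so Day 96 also serves as the nominal PEA day for a 6-month follow-up.

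**2. Gap between the end of the V0 to V2 table and the last dose.** Share of treatment time = gap ÷ day of last dose.
- Nominal: 6 ÷ 96 = 6.25%
- Maximum gap, catheterisation on Day 90: 7 ÷ 97 = 7.2%
- Maximum gap, catheterisation on Day 120: 7 ÷ 127 = 5.5%
- At three doses a day, 7 days is about 3 × 7 = 21 doses.

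**3. Dose level in the gap.** Going from 1 mg to 2.5 mg takes (2.5 − 1.0) ÷ 0.5 = 3 steps. With uninterrupted two-weekly increases the top level starts on Day 1 + 3 × 14 = Day 43. Days 43 to 97 are 55 days, so the 7 days are 7 ÷ 55 = 12.7% of the time at the top level for such a patient.

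**4. What is left for the longer table.** From Visit 2 to Visit 4: 276 − 90 = 186 days, nominally 6 on drug and 180 after surgery. Subtracting the V0 to V2 table from the V0 to V4 table recovers event counts for that interval. It does not recover patient counts, because a patient with events in both periods is counted once in each table and cancels out.

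**5. What other tables already show**

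| AESI as defined in SAP 9.1.7 | V0 to V3 tables (9.1.1 to 9.1.6) | Surgery-related complications (8.2.3.2, 13.3) |
|---|---|---|
| Hypotension (one preferred term) | Shown | None |
| Syncope (one preferred term) | Shown | None |
| Haemoptysis (one preferred term) | Shown | Only if it needs intervention |
| Myocardial infarction (two terms) | Separate terms, not the group | None |
| Stroke (three terms) | Separate terms, not the group | Inside a combined neurological item |
| Haemorrhage (standardised query) | Separate terms, not the group | Blood loss over 1 L in 12 hours; airway bleed needing ECMO |

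The V0 to V3 tables start at the first visit, so they include operative events without separating them from earlier ones. Counts for separate terms cannot simply be added to give patients per group.

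**The case against.** A reader might infer that nothing in the SAP isolates the operation. The documents do not support that. SAP 8.2.3.2 tabulates surgery-related complications by arm in the PEA set, with Fisher tests, and SAP 8.3 adds in-hospital mortality. Nor is it right that hypotension near surgery is invisible: it is a line in the V0 to V3 preferred-term tables. No event is lost either, since SAP 9.1 lists every adverse event with its start and end dates.

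The gap of up to 7 days is also not certain. The SAP never says where V2 ends, and SAP 3.2.2, 8.2.3 and 13.1 place perioperative findings at Visit 2, while the protocol's schedule, as it reads in the available text, marks them under Visit 3. If V2 takes in the operation, the gap closes. SAP 3.1 also labels the treatment period as Day 1 through Day 90, so a cut at Visit 2 has some textual basis. A preoperative cut that keeps surgical bleeding and hypotension out of the drug comparison is a defensible choice, and all analyses are exploratory.

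These points narrow the concern but do not remove it. If V2 includes surgery, operative events enter the shorter table without being separated. If it does not, the last days on drug are left out. The SAP explains neither choice. The Day 90 label sits in the same paragraph that continues dosing to the morning of PEA. The complications table uses narrower or differently grouped definitions for three AESIs and has no item for the other three. ECMO for haemodynamic support and prolonged inotropes are not substitutes for hypotension as an AESI.

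**Conclusion.** The point stands in limited form. With V2 read as the catheterisation visit, the shorter AESI window ends 0 to 7 days, nominally 6, before the last dose: 6.25% of treatment time nominally, 7.2% at most. It therefore matches neither the double-blind treatment phase named in protocol 7.8.4 nor the V0 to V3 cut used for every other adverse event table, and the difference is not declared in SAP section 11.

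Whichever way V2 is read, no AESI table separates the perioperative period. Two specific gaps remain after the other tables are counted:
- The haemorrhage query and the grouped infarction and stroke terms have no table that can be relied on to take in the operation and stop near it.
- Hypotension, myocardial infarction and syncope have no table confined to the perioperative period.

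This is a reporting weakness against a stated secondary objective. It does not affect sample size, the primary analysis or the error rate.

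**What to change.** In SAP 9.1.7, replace the visit labels with date-based windows that do not overlap before follow-up, plus the whole-study table:
- (a) First dose to the start of PEA; for patients who stop drug early or have no PEA, first dose to last dose.
- (b) Start of PEA to a defined end such as hospital discharge (or death in hospital), for patients who had PEA.
- (c) The whole study to Visit 4.

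Assign each surgery-day event once, to (a) or (b), by its onset time relative to the start of PEA. Protocol 6.3.1.3 already collects time of onset. The documents do not say whether the clock time at which PEA starts is recorded, so confirm this and state a rule for missing times. Discharge is a safer end point than Visit 3, which has no stated window and falls nominally on the same day as PEA (Day 96). The discharge date is needed anyway for length of stay.

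In the same revision:
- State whether V2 includes the operation, and reconcile SAP 8.2.3 and 13.1 with the protocol's schedule.
- Reconcile SAP 4.4, which limits the medication subgroups to V0 to V2, with SAP 9.1.1 to 9.1.6, which run the same subgroups to V3.
- Record the chosen safety windows in SAP section 11 where they differ from protocol 7.8.4.

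The cost is SAP wording and one extra set of table columns, with no change to study conduct. The downside is small counts in window (b), which should be presented descriptively.
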